### 3.0 Study Design

We propose to conduct a 2-arm, parallel, pragmatic, multi-centre, open-label randomized controlled trial to determine the effect of therapeutic anticoagulation on the composite outcome of ICU admission, invasive mechanical ventilation or death in hospitalized patients admitted for COVID-19. Eligible participants will be randomized to one of two treatment regimens, receiving either therapeutic anticoagulation or standard care until discharged from hospital, death or day 28. If the patient is admitted to the ICU or requiring ventilatory support, we recommend continuation of the allocated treatment as long as the treating physician is in agreement. Randomization will be stratified by site and age (>65 versus ≤65 years) using a 1:1 computer-generated random allocation sequence with variable block sizes. Randomization will occur within the first 5 days (i.e. 120 hours) of participant hospital admission. However, it is recommended that randomization occurs as early as possible after hospital admission. Central randomization using an interactive web response system will ensure allocation concealment. This is an open label study. Blinding of participants, clinical research staff, and clinicians is not possible due to the nature of the intervention. However, the biostatisticians will be blinded at the data analysis phase. Given the objective nature of the primary outcome and the need for pragmatic approaches for this rapid response trial, an independent, blind clinical events committee is not planned (17). See Figure 1 for study schematic.

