**Prophylactic Dose Anticoagulation**

CrCl	BMI	Enoxaparin	Dalteparin	Tinzaparin	Fondaparinux	Unfractionated Heparin (UFH)
$\geq 30$	<40	40 mg SC q24h	5000 units SC q24h	4500 U SC q24h	2.5 mg SC q24h	5000 units SC q8-12h
	$\geq 40$	40 mg SC q12h	5000 units SC q12h	9000 (+/- 1000) U SC q24h	not applicable	7500 units SC q8h
<30	<40	UFH 5000 units SC q8-12h or LMWH per hospital protocol taking BMI into consideration as above				
	$\geq 40$	UFH 7500 units SC q8h or LMWH per hospital protocol taking BMI into consideration as above				

Abbreviations: CrCl = creatinine clearance; BMI = body mass index

Type and doses of thromboprophylactic LMWH or UFH will be recorded in the case report forms. Concomitant medications and co-enrollment of other COVID-19 trials will also be recorded.

Full therapeutic dose anticoagulation (therapeutic dose UFH or LMWH) is permitted as rescue therapy in the event of suspected or confirmed thromboembolism. Additional rescue therapy, in the form of thrombolysis (with tissue plasminogen activator), is also permitted if deemed clinically warranted by the treating clinical team.

Institutional drug stock will be used, and the institutional pharmacy will be responsible for labelling and distribution. No repackaging of drugs will occur.

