**Secondary outcomes (secondary endpoints), evaluated up to day 28, include:**

- 1) All-cause death;
- 2) Composite of ICU admission or all-cause death;
- 3) Composite of mechanical ventilation or all-cause death;
- 4) Major bleeding as defined by the ISTH Scientific and Standardization Committee (ISTH-SSC) recommendation (21);
- 5) Red blood cell transfusion ( $\geq 1$  unit);
- 6) Transfusion of platelets, frozen plasma, prothrombin complex concentrate, cryoprecipitate and/or fibrinogen concentrate;
- 7) Renal replacement therapy defined as continuous renal replacement therapy {CRRT} or intermittent hemodialysis {IHD};
- 8) Hospital-free days alive;
- 9) ICU-free days alive;
- 10) Ventilator-free days alive;

- 11) Organ support-free days alive (see Appendix 4 for definition);
- 12) Venous thromboembolism (defined as symptomatic or incidental, suspected or confirmed via diagnostic imaging and/or electrocardiogram where appropriate recognizing that access to diagnostic imaging may be limited in the midst of the COVID-19 pandemic, however confirmatory testing at a later date once exposure risk/personal protective utilization is not an issue is encouraged);
- 13) Arterial thromboembolism (defined as suspected or confirmed via diagnostic imaging and/or electrocardiogram where appropriate recognizing that access to diagnostic imaging may be limited in the midst of the COVID-19 pandemic, however confirmatory testing at a later date once exposure risk/personal protective utilization is not an issue is encouraged);
- 14) Heparin induced thrombocytopenia;
- 15) Trajectories of COVID-19 disease-related biomarkers.

Outcome measures will be obtained from participants' hospital medical records and where applicable through a telephone follow-up, as outlined in Table 5: Study Schedule of Events. The use of BIPAP or CPAP at night or when sleeping for sleep apnea is not considered non-invasive mechanical ventilation or organ support for the purpose of this trial.

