defined via diagnostic imaging and/or electrocardiogram where appropriate and possible; AE/SAE will be recorded on any day.

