2.2.1 Secondary Outcomes

- 1) Proportion of all-cause death within the first 28 days post-randomization.
- 2) Proportion of subjects with the composite outcome of ICU admission or all-cause death within the first 28 days post-randomization.
- 3) Proportion of subjects with the composite outcome of invasive or non-invasive mechanical ventilation or all-cause death within the first 28 days post-randomization.

- 4) Proportion of subjects with major bleeding, as defined by the ISTH Scientific and Standardization Committee (ISTH-SSC), within the first 28 days post-randomization.
- 5) Proportion of subjects with red blood cell transfusion ≥ 1 unit within the first 28 days post-randomization.
- 6) Proportion of subjects who experienced the following: transfusion of platelets, frozen plasma, prothrombin complex concentrate, cryoprecipitate and/or fibrinogen concentrate within the first 28 days post-randomization.
- 7) Proportion of subjects who had renal replacement therapy defined as continuous renal replacement therapy (CRRT) or intermittent hemodialysis (IHD) within the first 28 days post-randomization.
- 8) Hospital-free days alive up to day 28 post-randomization.
- 9) ICU-free days alive up to day 28 post-randomization.
- 10) Ventilator-free days alive up to day 28 post-randomization.
- 11) Organ support-free days alive up to day 28 post-randomization.
- 12) Proportion of subjects who had venous thromboembolism defined as symptomatic or incidental, suspected or confirmed via diagnostic imaging and/or electrocardiogram where appropriate, recognizing that access to diagnostic imaging may be limited in the midst of the COVID-19 pandemic. Confirmatory testing at a later date once exposure risk/personal protective utilization is not an issue is encouraged within the first 28 days post-randomization.
- 13) Proportion of subjects who had arterial thromboembolism defined as suspected or confirmed via diagnostic imaging and/or electrocardiogram where appropriate, recognizing that access to diagnostic imaging may be limited in the midst of the COVID-19 pandemic. Confirmatory testing at a later date once exposure risk/personal protective utilization is not an issue is encouraged within the first 28 days post-randomization.
- 14) Proportion of subjects with heparin induced thrombocytopenia within the first 28 days post-randomization.
- 15) D-dimer, a COVID-19 disease-related biomarker at day 2 $+$ /- 24 hours post-randomization.

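### The thromboembolism outcomes pool suspected with confirmed events in an open-label trial without blind adjudication, and no planned analysis separates the two

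*SAP*

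**What the plan says.** - **Outcome definition.** SAP 2.2.1 item 12 counts venous events that are "symptomatic or incidental, suspected or confirmed via diagnostic imaging and/or electrocardiogram where appropriate". Item 13 covers "arterial thromboembolism defined as suspected or confirmed via diagnostic imaging and/or electrocardiogram where appropriate". The protocol uses the same definition in its synopsis, section 2.0 and section 6.3. SAP 2.2.1 and protocol sections 2.0 and 6.3 give the reason: imaging may be hard to obtain during the pandemic.
- **Confirmation.** It is not required: "Confirmatory testing at a later date once exposure risk/personal protective utilization is not an issue is encouraged".
- **Blinding and adjudication.** Protocol 3.0 states: "Blinding of participants, clinical research staff, and clinicians is not possible due to the nature of the intervention". The biostatisticians are blinded at analysis. The same section plans no independent blind events committee and justifies this by the objectivity of the primary outcome and the need for a pragmatic design.
- **Schedule of events.** Footnote 8 of protocol Table 5 describes venous or arterial thromboembolism as "defined via diagnostic imaging and/or electrocardiogram where appropriate and possible". It does not list suspected events.
- **Link to treatment.** Protocol 5.2, in the text after Table 3, says full-dose anticoagulation "is permitted as rescue therapy in the event of suspected or confirmed thromboembolism".
- **Analysis.** SAP 4.3 tests the binary secondary outcomes as defined, with a chi-squared test and an odds ratio. SAP 4.5 varies follow-up, eligibility, per-protocol status, the link function and calendar time. Protocol 7.2 calls the secondary outcomes exploratory, without multiplicity adjustment.

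**The concern.** Whether a clot is suspected is a bedside judgement, and here it is made by people who know whether the patient is on a therapeutic or a prophylactic dose. It is plausible that the threshold for suspicion differs between arms, and a suspicion can also open access to full-dose treatment in the control arm. Blinding the statisticians does not help, because the label is fixed before they see the data.

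The protocol's argument for doing without adjudication rests on the primary outcome. Thromboembolism is not a component of that composite, so the argument does not carry over.

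At stake is how far outcomes 12 and 13 can be interpreted. The protocol's Study Summary makes thromboembolism part of the rationale for anticoagulation, and SAP section 4 gives every outcome comparison an estimate, a 95% confidence interval and a p-value. These results will therefore be read. As the plan stands, a reader could not tell how much of any difference comes from unconfirmed events.

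**Working it through.** **1. The plan's own figure.** The documents state no rate and no power for thromboembolism. The only figure needed is the arm size of 231 (protocol 7.1: 462 in total, 50% vs 35%, 90% power, two-sided 0.05). The usual two-proportion formula, with mean rate 0.425, gives

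n = [1.96·√(2·0.425·0.575) + 1.2816·√(0.50·0.50 + 0.35·0.65)]² / 0.15² = (1.370 + 0.886)² / 0.0225 ≈ 226.2, so 227 per arm (454 in total).

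A Hwang-Shih-DeCani efficacy boundary with looks at 25%, 75% and 100% inflates this by 1.017 when gamma is −4. Gamma is an assumption, since the documents give none. Then 227 × 1.017 ≈ 230.9, so 231 per arm. The planned 462 reproduces, and nothing below changes it.

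**2. Is there an analysis by confirmation status?** SAP 4.3 uses the pooled outcome. SAP 4.5 lists exclusions for incomplete follow-up, for ineligibility and for both, a repeat in the per-protocol set, the identity-link model, and a time-by-treatment spline. None uses confirmation status.

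**3. Table 5 against the outcome definition.** SAP 2.2.1 and protocol 6.3 include suspected events explicitly. Footnote 8 names imaging and ECG, omits suspected events, and adds a qualifier about what is appropriate and possible. The wordings differ. The qualifier leaves room for events that could not be imaged, so the two can be read together.

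**4. Illustration of size.** Every rate here is an assumption. Let c be the confirmed rate, equal in both arms (no true effect), and let s_E and s_C be the suspected-only rates in the experimental and control arms.

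OR = [(c + s_E)/(1 − c − s_E)] / [(c + s_C)/(1 − c − s_C)]

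With c = 3%, s_E = 1% and s_C = 3%: OR = (0.04/0.96)/(0.06/0.94) = 0.0417/0.0638 = 0.65.

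| c | 1% vs 3% | 1% vs 2% | 0.5% vs 2% |
|---|---|---|---|
| 2% | 0.59 | 0.74 | 0.62 |
| 3% | 0.65 | 0.79 | 0.69 |
| 5% | 0.73 | 0.85 | 0.77 |

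The range is 0.59 to 0.85. If s_E = s_C, the odds ratio is 1.00. If the imbalance ran the other way, it would exceed 1.

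**5. How visible would it be at 231 per arm?** In the 3% case the expected counts are 231 × 0.04 = 9.2 and 231 × 0.06 = 13.9. The standard error of the log odds ratio is √(1/9.24 + 1/221.76 + 1/13.86 + 1/217.14) = 0.435, so the 95% interval around 0.65 runs from about 0.28 to 1.53. The chance of a two-sided p < 0.05 in favour of the experimental arm is 2.5% without imbalance. With suspected-only rates of 1% vs 3% it is about 19% for c = 2% and 13% for c = 5%. Simulation of those two settings gave 19% and 13%.

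**The case against.** The strongest reply is that the definition is deliberate, its reason is given, and the outcomes are exploratory. Thromboembolism enters neither the primary composite nor the stopping criteria in protocol 7.3, which use conditional power, major bleeding and death. The assumed asymmetry produces the odds ratio of 0.65, and an interval of 0.28 to 1.53 would not persuade a careful reader of an effect. The eCRF is not among the documents and may already record confirmation status. All of this stands. It limits the weight of the point, but it does not supply the missing analysis.

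Three stronger readings are tempting and should be resisted.

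- A reader might infer that Table 5 contradicts the outcome definition. It does not: footnote 8 omits suspected events, but its qualifier allows for cases where imaging was not possible. This is a difference in wording to be reconciled.
- A reader might infer that the comparison is biased toward the experimental arm. Unblinded clinicians and rescue on suspicion make that possible, but no text shows that labelling will differ by arm.
- A reader might infer that a confirmed-only analysis would expose or remove the bias. The same unblinded clinicians decide who is imaged, and item 12 also counts incidental findings, so confirmed events can be ascertained unequally too. The confirmed-only odds ratio of 1.00 in the illustration follows from assuming equal confirmed rates.

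**Conclusion.** The concern holds in a limited form. Outcomes 12 and 13 mix unconfirmed with confirmed events, the people labelling them know the allocation, the stated reason for having no blind committee does not cover these outcomes, and no planned analysis separates the two kinds of event. Differential suspicion could therefore bias these two comparisons, and the planned outputs would not show how far a difference depends on unconfirmed events.

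The size is unknown. Odds ratios of 0.59 to 0.85 with no true effect follow from assumed confirmed rates of 2% to 5% and assumed suspected-only gaps of 1 to 2 percentage points. They illustrate sensitivity and are not estimates for this trial. The primary analysis and the sample size of 462 are untouched. The change is worth making because it costs so little.

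**What to change.** Keep the pandemic-adapted definition and make these changes.

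1. **SAP 4.3:** pre-specify a sensitivity analysis of outcomes 12 and 13 restricted to events confirmed by imaging or ECG, including those confirmed by later testing. Report it beside the pooled result, with suspected-only counts by arm.
2. **Data capture:** check that the eCRF records suspected or confirmed status for each event, and add the field if it does not.
3. **Protocol Table 5, footnote 8:** reconcile it with the outcome definition in section 6.3.

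The cost is one SAP sentence, a few table rows, a footnote edit and possibly one eCRF field. The confirmed-only row will have fewer events and a wider interval. The SAP text should present it as a check that lessens dependence on unblinded judgement, since decisions about whom to image remain unblinded.

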3. STUDY DESIGN

3.1 Study Design

This is an open-label, parallel, two-arm randomized controlled trial (RCT) comparing therapeutic anticoagulation with LMWH or high dose nomogram of UFH (experimental group) to standard care (control group) to determine the effect of therapeutic anticoagulation on the composite outcome of ICU admission, mechanical ventilation (non-invasive or invasive) or death in hospitalized patients admitted for COVID-19.

3.2 Study Cohort

The study cohort consists of hospitalized adults admitted for COVID-19 prior to the development of critical illness. Individuals with the following characteristics are excluded: bleeding risk or risk of transfusion generally considered unacceptable, absolute indication for therapeutic anticoagulation, and already met components of the primary outcome.

3.2.1 Intent-to-Treat (ITT) Cohort

The Intent-to-Treat (ITT) cohort will consist of all randomized subjects. The primary analysis will be conducted on the ITT cohort according to the treatment group to which the subjects were randomized. In the rare event that a subject does not have a 28-day assessment and they were event-free and discharged alive prior to day 28, they will be assumed to still be event-free up to day 28.

3.2.2 Per-Protocol (PP) Cohort

The Per-Protocol (PP) cohort will consist of all eligible randomized subjects who received their intervention as allocated during the first 48 hours after randomization. The PP analysis will exclude subjects who did not receive their allocated treatment during the first 48 hours after randomization.

3.3 Treatment Definition

There are two treatment groups in the study. Subjects are randomized (1:1) within the age strata (≤ 65 and > 65) to receive (i) therapeutic doses of LMWH or high dose nomogram of UFH (experimental group) or (ii) standard care with thromboprophylactic doses of LMWH or UFH (control group).

4. STATISTICAL ANALYSIS

Categorical data will be summarized by counts and percentages, and continuous variables by means and standard deviations, or medians and interquartile ranges. All outcome comparisons will include a treatment effect estimate along with a 95% confidence interval. All outcome comparisons will include a p-value calculated using an appropriate test.

4.2 Primary Outcome Analysis

The primary analysis will compare the proportions of subjects experiencing the composite outcome within 28 days after randomization between the 2 treatment arms (therapeutic doses of LMWH or high dose nomogram of UFH versus standard care). Difference in proportions and the 95% confidence interval will be reported. A Chi-squared test of independence will be conducted to obtain the p-value. Since randomization was stratified by age a logistic regression model will also be fit to obtain and test the treatment effect adjusting for age. These two complementary analyses are being performed since an adjusted analysis result in a different interpretation of the treatment effect (conditional) versus the unadjusted (marginal or population averaged). Although the protocol specifies binomial models with an identity link, these were found to not converge by the unblinded statistician while preparing DSMB reports. Therefore, the more stable logistic regression model will be used. Since two interim analyses were conducted, the level of significance at which the Chi-squared test of independence is conducted is 0.048 (two-sided).

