- 11) known history of heparin-induced thrombocytopenia;
- 12) known allergy to UFH or LMWH;
- 13) admitted to the intensive care unit at the time of screening;
- 14) treated with non-invasive positive pressure ventilation or invasive mechanical ventilation at the time of screening (of note: high flow oxygen delivery via nasal cannula is acceptable and is not an exclusion criterion);
- 15) Imminent death according to the judgement of the most responsible physician;

- 16) enrollment in another clinical trial of antithrombotic therapy involving pre-intensive care unit hospitalized patients.

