### **7.0 Statistical Plan**

#### ***7.1 Sample Size Calculation***

462 patients (231 per group) are needed to detect a 15% risk difference, from 50% in the control group to 35% in the experimental group (2), with power of 90% at a two-sided alpha of 0.05. No attrition is expected. This calculation takes 2 interim analyses into account. There is no inflation to account for losses to follow-up because we expect these to be very infrequent, and given the nature of the trial, included patients, and outcomes, we may conclude an absence of the primary outcome in patients discharged alive from hospital before 28 days with missing outcome data at day 28.

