**Table 5. Study Schedule of Events**

	Screening 1,2,\$	Randomization 1,2,\$ (Day 1)	Day 3 \$	Day 7 \$	Day 14 \$	Day 28 \$
Informed Consent	X					
Inclusion/Exclusion	X					
Lowest oxygen saturation (%) on room air	X					
Maximum supplemental oxygen (FiO 2 ) β	X*	X*	X*	X*	X*	X*
Concomitant Medications (including other COVID-19 trial treatments)	X*	X*	X*	X*	X*	X*
Demographics (age, sex, race/ethnicity φ )	X					
Medical History (including smoking, date of COVID-19 symptom onset)	X*					
Height	X**					
Weight	X**					
Dose and frequency of therapeutic anticoagulation administered (treatment arm)		X*	X*	X*	X*	X*
Dose and frequency of LMWH or UFH at thromboprophylactic doses (standard care arm)		X*	X*	X*	X*	X*
Complete Blood Count		X*	X*	X*	X*	X*
Ferritin		X*	X*	X*	X*	X*
D-Dimer	X*	X*	X***	X*	X*	X*
PT		X*	X*	X*	X*	X*
aPTT 		X*	X*	X*	X*	X*
Anti-Xa for UFH 		X*	X*	X*	X*	X*
Anti-Xa for LMWH		X*	X*	X*	X*	X*
INR		X*	X*	X*	X*	X*

Fibrinogen		X*	X*	X*	X*	X*
Lactate dehydrogenase		X*	X*	X*	X*	X*
Troponin		X*	X*	X*	X*	X*
C-Reactive Protein		X*	X*	X*	X*	X*
Creatinine		X*	X*	X*	X*	X*
ALT		X*	X*	X*	X*	X*
Heparin-Platelet Factor 4 Immunoassay		X*	X*	X*	X*	X*
Blood group		X ∞				
Primary outcome assessment 		X*	X*	X*	X*	X*
Length of Hospital Stay		X*	X*	X*	X*	X*
Bleeding Event 		X*	X*	X*	X*	X*
Red Blood Cell transfusion 6a and/or transfusion of any hemostatic blood product/component 6b		X*	X*	X*	X*	X*
Renal replacement therapy 		X*	X*	X*	X*	X*
Organ support (see Appendix 4)		X*	X*	X*	X*	X*
Venous or arterial thromboembolism 		X*	X*	X*	X*	X*
AE/ SAE Assessment 		X*	X*	X*	X*	X*
Optional Biobanking		X†	X†	X†	X†	

\* collected through standard of care when available in the chart;

\*\* height and weight to be collected from the patient's chart or obtained verbally from the patient;

\*\*\* D-dimer will be drawn once on day 2 after randomization (+/- 24 hours); if collected through standard of care, study specific D-Dimer is not needed);

See Appendix 3 for FiO2 for nasal cannula and Venturi mask;

Race/ethnicity of participant collected given known ethnic variation of D-dimers (categories defined in Appendix 1 (23); to obtain verbally from the patient);

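### The supportive adjusted analysis of the primary outcome uses age alone, although oxygen status and D-dimer are recorded at screening: a missed improvement, not an error

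*SAP*

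**What the plan says.** SAP 4.2 compares the proportions with the primary composite by 28 days. It reports the difference with a 95% CI and takes the p-value from a chi-squared test at a two-sided level of 0.048. It then adds a complementary model: "Since randomization was stratified by age a logistic regression model will also be fit to obtain and test the treatment effect adjusting for age". The reason given is that age was a stratification factor. The SAP notes that the adjusted (conditional) and unadjusted (marginal) effects are interpreted differently. It also reports that the protocol's identity-link model did not converge, which is why logistic regression replaces it.

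Protocol Table 5 has a row for "Lowest oxygen saturation (%) on room air" in the Screening column. Maximum FiO2 and D-dimer are listed there too, marked as chart data collected when available. Inclusion criterion 3 (Protocol 4.0) is built on D-dimer and room-air saturation. Exclusion criterion 14 notes that "high flow oxygen delivery via nasal cannula is acceptable and is not an exclusion criterion". SAP 4.3 already defines log(D-dimer/ULN) for another outcome.

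**The concern.** The composite is ICU admission, non-invasive or invasive ventilation, or death. Entry runs from patients who qualify on D-dimer alone, at any saturation, to patients already on high-flow nasal oxygen, so starting respiratory severity can differ widely. Randomization is stratified by site and age (Protocol 3.0), so neither the design nor the adjusted model accounts for oxygen status or D-dimer. The investigators themselves treat these variables as important: Protocol 1.0 cites D-dimer as strongly associated with mortality, and the tertiary objective names D-dimer and hypoxia.

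Two things are at stake in the supportive analysis. It gives up precision that the recorded data could supply. And if the arms differ by chance in baseline oxygen need, the crude and age-adjusted results move together, except so far as age tracks oxygen need. In an open-label trial, readers will ask about such an imbalance, and a prespecified answer is more credible than a post hoc one.

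**Working it through.** **1. The plan's own sample size.** Protocol 7.1: "462 patients (231 per group) are needed" "to detect a 15% risk difference, from 50% in the control group to 35% in the experimental group" "with power of 90% at a two-sided alpha of 0.05". It adds that "No attrition is expected" and "This calculation takes 2 interim analyses into account".

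n per arm = [1.960·√(2·0.425·0.575) + 1.2816·√(0.50·0.50 + 0.35·0.65)]² / 0.15² = (1.370 + 0.886)² / 0.0225, which rounds up to 227. With Hwang-Shih-DeCani looks at 25% and 75% and gamma = −4 (assumed; the documents do not give gamma), the inflation is 1.0171. Then 227 × 1.0171 = 230.9, so 231 per arm and 462 in total. The stated figure is reproduced. Power with 231 per arm at 0.048 is 90.3%. The supportive model does not enter this figure.

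**2. Assumed prognostic strength.** The documents give no figure. Assume 30/50/20% of patients on no, low-flow and high-flow oxygen, with three sets of control risks. Share of variance explained: R² = Σw(p − p̄)² / [p̄(1 − p̄)].

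- 25/50/85%: p̄ = 0.495; 0.0432/0.2500 = 0.17
- 35/50/70%: p̄ = 0.495; 0.0147/0.2500 = 0.06
- 40/50/65%: p̄ = 0.500; 0.0075/0.2500 = 0.03

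**3. What adjustment does.** Simulated trials with 231 per arm, a common odds ratio set to give a 15-point marginal difference, and level 0.048. The models are without and with oxygen level; D-dimer and age are not in this simulation.

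| Assumed R² | Power, unadjusted | Power, adjusted | SE of log odds ratio | Variance of standardized risk difference, adjusted/unadjusted |
|---|---|---|---|---|
| 17% | about 90% | 94.6% | 0.191 → 0.215 | 0.83 |
| 6% | about 90% | 92.1% | 0.192 → 0.199 | 0.94 |
| 3% | about 90% | 90.9% | 0.191 → 0.195 | 0.96 |

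The SE of the log odds ratio rises in every row. Power still rises because the conditional odds ratio lies further from 1. Only the standardized risk difference gets a narrower interval.

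**4. In points.** At the planning rates, SE = √[(0.25 + 0.2275)/231] = 0.0455, so the 95% half-width is 1.96 × 4.55 = 8.9 points. Multiplying by √0.83 gives 8.1; by √0.96 gives 8.7.

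**5. Age, oxygen and D-dimer together.** A second simulation (3,000 trials of 462 per scenario) used continuous oxygen and D-dimer scores with correlation 0.3, and age >65 in 40% of patients. All of these are assumptions.

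| Total R² | Power, age only | Power, age + oxygen + D-dimer | Variance ratio of risk difference |
|---|---|---|---|
| 0.05 | 90.5% | 91.4% | 0.975 |
| 0.10 | 90.5% | 92.9% | 0.911 |
| 0.20 | 89.6% | 94.9% | 0.832 |
| 0.28 | 91.1% | 97.0% | 0.734 |

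With neither covariate prognostic, power was 90.0% with age only and 90.1% with all three, so nothing is lost. Age by itself adds almost nothing: 90.1% for chi-squared against 90.5% age-adjusted at R² 0.10.

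**6. Chance imbalance.** The shift in the crude difference due to oxygen mix alone has SD √(Σw(p − p̄)² × 2/231), using control risks. The size exceeded in 1 trial in 20 is 1.96·√(0.0432 × 2/231) = 3.8 points at R² 17%, 2.2 points at 6% (variance 0.0147) and 1.6 points at 3% (variance 0.0075).

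**The case against.** The strongest case for leaving the plan alone has several parts.

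- **The confirmatory result is not affected.** A reader might infer that the trial loses power on its primary test. The documents do not support that: the p-value comes from the unadjusted chi-squared test at 0.048, and the power gains above belong to the supportive test. This stands.
- **Adding covariates does not narrow the odds-ratio interval.** A reader might expect the adjusted logistic model to be more precise as it stands. The interval for the log odds ratio widens and the target becomes a different conditional effect. This stands, and it is why standardization has to be part of the change.
- **Chance imbalance is not bias.** The type I error of a randomized comparison already allows for it. Correct; adjustment helps precision and interpretation, not validity.
- **Age was chosen on principle, and is not the only covariate anywhere in the SAP.** It was a stratification factor. SAP 4.4 has logistic subgroup models, including baseline D-dimer, and SAP 4.5 has a calendar-time model. But none of these gives an overall treatment effect adjusted for baseline severity. Site, the other stratification factor, is also absent from the adjusted model.
- **The size is assumed.** No figure in the documents shows how much oxygen status or D-dimer predicts this composite. The D-dimer evidence cited in Protocol 1.0 concerns mortality in another cohort, and entry here is already restricted to raised D-dimer, which may narrow its prognostic range. The weaker scenarios gain only 1 to 2 points of power. This limits the size of the point but does not remove it.
- **The data are not perfectly clean.** FiO2 and D-dimer are chart values, and screening and randomization may fall on the same day. A screening maximum is therefore not automatically a pre-randomization value. This stands and is dealt with in the change proposed.

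**Conclusion.** The point holds as a missed improvement in the supportive analysis. SAP 4.2 adjusts for age only, while likely stronger predictors are scheduled for collection at screening. Nothing here makes the chi-squared test invalid or the trial underpowered.

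If oxygen status explains 3% to 17% of outcome variance, standardizing over it cuts the variance of the risk difference by about 4% to 17% (95% half-width from 8.9 to between 8.7 and 8.1 points). Power of the adjusted test goes from about 90% to between 91% and 95%. The direction of the gain is secure provided the covariates are prognostic, and there is practically no loss if they are not. The size rests on an assumed oxygen mix and assumed risks. The share due to D-dimer has not been isolated.

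**What to change.** Keep the chi-squared test at 0.048 as the primary analysis. In SAP 4.2:

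1. Fit the supportive logistic model with age, screening oxygen status (maximum FiO2 or lowest room-air saturation; choose one in advance) and baseline log(D-dimer/ULN) as defined in SAP 4.3. Use only values recorded before randomization. The Day 1 column does not guarantee this, nor does the Screening column when both fall on one day.
2. From that model, report the covariate-standardized risk difference with its 95% CI beside the conditional odds ratio. This is on the scale SAP 4.2 already reports and avoids the identity-link convergence problem.
3. Extend SAP 4.6, whose baseline imputation covers age only, with a simple rule for missing oxygen and D-dimer values.
4. Have blinded staff fix the covariate list and coding, and document this, because SAP 4.2 records that an unblinded statistician has already fitted models for DSMB reports.

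The cost is a few sentences of SAP text and a short standardization step, with no new data collection. The small downside is handling a few missing chart-derived values.
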